7.2 Visit 2 (Week 0± 5 days Baseline)

- a) UAS7 score assessment
- b) ISS score assessment
- c) Nucala 200mg injection
- d) Dispense epinephrine auto-injector

7.3 Visit 3 (Week 2± 5 days)

- a) UAS7 score assessment
- b) ISS score assessment
- c) Nucala 200mg injection
- d) Screen for adverse events

7.4 Visit 4 (Week 4 ± 5 days)

- a) UAS7 score assessment
- b) ISS score assessment
- c) Nucala 200mg injection
- d) Screen for adverse events

Visit 5 (Week 6 ± 5 days)

- a) UAS7 score assessment
- b) ISS score assessment
- c) Nucala 200mg injection
- d) Screen for adverse events

7.5 Visit 6 (week 8± 5 days)

- a) UAS7 score assessment
- b) ISS score assessment
- c) Nucala 200mg injection
- d) Screen for adverse events

7.6 Visit 7 (week 10± 5 days)

- a) UAS7 score assessment
- b) ISS score assessment
- c) UCT score assessment
- d) 4mm punch skin biopsy if residual disease
- e) Collect UAS log book
- f) Blood work: CBC with differential, serum IgE level, chronic urticaria index, IgE Fc receptor antibody functional assay
- g) Screen for adverse events
- h) Photograph biopsy site

Week	Wk -2 screen	Wk 0 baseline	Wk 2	Wk 4	Wk 6	Wk 8	Wk 10
Visit	1	2	3	4	5	6	7
Consent/Enroll	X						
Distribute log book	X						
Collect log book							X
Cbc with Diff	X						X
Serum IgE	X						X
CIU index	X						X
IgE Fc Recept Ab	X						X
Urine HCG	X						
UCT		X					X
UAS		X	X	X	X	X	X
ISS		X	X	X	X	X	X
Skin Biopsy	X						X***
Nucala Inj*		X	X	X	X	X	
Cetirizine (Zyrtec) Dispense	X						
Epinephrine auto-injector Dispense		X					
AE Screening**		X	X	X	X	X	X
	
* Nucala Inj = denotes Nucala SQ injection during a visit ** AE Screening = protocol directed screening for adverse events ***At end of study if subjects have residual disease, will biopsy, as necessary, to check for lesional eosinophil tissue density
						

8 Statistical Plan

8.1 Sample Size Determination

The statistical methods proposed in the study were reviewed with a Mayo staff statistician who also assisted in a formal power analysis. Demographic and laboratory characteristics will be analyzed using descriptive statistics. A paired t-test will be used to evaluate mean differences before and after treatment at a $p=0.05$ significance level. The primary endpoint of the study is the UAS7. A 10 point change in the UAS7 has been reported to be the minimal clinically significant difference in therapeutic trials for urticaria. The study is powered at 99% to detect a 10 point change in the UAS7 at a 5% significant level with the proposed accrual target of 20 patients.

8.2 Statistical Methods

Descriptive Statistics

Continuous variables will be summarized using the sample mean, median, standard deviation, interquartile range, and range. Categorical variables will be summarized using number and percentage of patients

Handling of Missing Data

This is a prospective study and therefore we do not anticipate any missing data. In the event of any unexpected missing data, no attempt to impute this missing data will be made; missing data will simply be treated as missing in the statistical analysis.

Multiplicity

Since this is an exploratory pilot study, no adjustment for multiple testing is needed.

Interim Analysis

There will not be any interim analysis given the low risk profile of the study formulation.

8.3 Subject Population(s) for Analysis

Each participant who received the study drug will be included in the primary analysis regardless of study withdrawal for any reason. In the event of any study withdrawals, in secondary analysis we will examine the sensitivity of our results to the exclusion of patients who withdrew.

9 Safety and Adverse Events

9.1 Definitions

Unanticipated Problems Involving Risk to Subjects or Others (UPIRTSO)

Any unanticipated problem or adverse event that meets the following three criteria:

- Serious: Serious problems or events that results in significant harm, (which may be physical, psychological, financial, social, economic, or legal) or increased risk for the subject or others (including individuals who are not research subjects). These include: (1) death; (2) life threatening adverse experience; (3) hospitalization - inpatient, new, or prolonged; (4) disability/incapacity - persistent or significant; (5) birth defect/anomaly; (6) breach of confidentiality and (7) other problems, events, or new information (i.e. publications, DSMB reports, interim findings, product labeling change) that in the opinion of the local investigator may adversely affect the rights, safety, or welfare of the subjects or others, or substantially compromise the research data, **AND**
- Unanticipated: (i.e. unexpected) problems or events are those that are not already described as potential risks in the protocol, consent document, not listed in the Investigator's Brochure, or not part of an underlying disease. A problem or event is "unanticipated" when it was unforeseeable at the time of its occurrence. A problem or event is "unanticipated" when it occurs at an increased frequency or at an increased severity than expected, **AND**
- Related: A problem or event is "related" if it is possibly related to the research procedures.

Adverse Event

An untoward or undesirable experience associated with the use of Nucala in a research subject. Initial screening for AE will include non-directed questioning of the patient at each follow-up visit during the study period.

Serious Adverse Event

Adverse events defined as serious will the following:

- death
- life threatening adverse experience
- hospitalization
- inpatient, new, or prolonged; disability/incapacity
- persistent or significant disability or incapacity

- birth defect/anomaly

and any problems/events that in the opinion of the sponsor-investigator may have adversely affected the rights, safety, or welfare of the subjects or others, or substantially compromised the research data.

All adverse events that do not meet any of the criteria for serious, will be regarded as **non-serious adverse events** as previously defined above.

Adverse Event Reporting Period

For this study, the study treatment follow-up period is defined as the last scheduled visit.

Preexisting Condition

A preexisting condition is one that is present at the start of the study. A preexisting condition will be recorded as an adverse event if the frequency, intensity, or the character of the condition worsens during the study period.

General Physical Examination Findings

At screening, any clinically significant abnormality should be recorded as a preexisting condition. At the end of the study, any new clinically significant findings/abnormalities that meet the definition of an adverse event will also be recorded and documented as an adverse event.

Post-study Adverse Event

All unresolved adverse events should be followed by the sponsor-investigator until the events are resolved, the subject is lost to follow-up, or the adverse event is otherwise explained. At the last scheduled visit, the sponsor-investigator should instruct each subject to report, to the sponsor-investigator, any subsequent event(s) that the subject, or the subject's personal physician, believes might reasonably be related to participation in this study.

Abnormal Laboratory Values

Any clinical laboratory abnormality that can reasonably be related to the administration of Nucala should be documented as an adverse event.

Hospitalization, Prolonged Hospitalization or Surgery

Hospitalization, prolonged hospitalization, or surgery is to be reported as an adverse event if it can reasonably be related to use of Nucala.

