5.4 Early Withdrawal of Subjects

5.4.1 When and How to Withdraw Subjects

Patients are free to withdraw at any time and for whatever reason. No data will be collected for withdrawn subjects. Withdrawn subjects may be replaced within the 6-month accrual period. There will be no follow-up for withdrawn subjects. Pre-specified reasons for discontinuing include, but are not limited to, the following:

- Patient Request: Patient decided that he/she did not want to continue (for any reason)
- Adverse Event: Patient experienced a related or unrelated event that would interfere with the study objectives/evaluation
- Lost to Follow-up: Patient did not come in for a visit and could not be reached by phone
- Treatment Failure: If in the Principal Investigator and/or Investigators' judgment, the patient's condition required another form of treatment
- Inclusion/Exclusion Discrepancy/Violation: Patient should not have been enrolled
- Noncompliance: Patient is not complying with the protocol requirements (i.e. visit schedule, dosing, regimen, etc.); a patient is to be withdrawn if he/she misses two consecutive visits
- Other: Any other reason

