9.2 Recording of Adverse Events

At each contact with the subject, the study team will seek information on adverse events by specific questioning and, as appropriate, by examination. Information on all adverse events should be

recorded immediately in the source document, and also in the appropriate adverse event section of the case report form (CRF). All clearly related signs, symptoms, and abnormal diagnostic, laboratory or procedure results will be recorded in the source document.

All adverse events occurring during the study period will be recorded. The clinical course of each event should be followed until resolution, stabilization, or until it has been ultimately determined that the study treatment or participation is not the probable cause. Serious adverse events that are still ongoing at the end of the study period must be followed up, to determine the final outcome. Any serious adverse event that occurs during the Adverse Event Reporting Period and is considered to be at least possibly related to the study treatment or study participation should be recorded and reported immediately.

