9.3.1 Sponsor-Investigator reporting: notifying the Mayo IRB

The Principal Investigator and/or Investigators will report, as soon as possible, but no later than 5 working days after first learning of the problem/event, to the Mayo Clinic IRB any UPIRTSOs and Non-UPIRTSOs according to the Mayo Clinic IRB Policy and Procedures.

Documentation of adverse events will include the following information collected in the adverse event section of the case report form (and entered into the research database):

- Subject's name:
- Medical record number:
- Disease:
- The date the adverse event occurred:
- Description of the adverse event:
- Relationship of the adverse event to the research:
- If the adverse event was expected:
- The severity of the adverse event (defined by a severity scale):
- If any intervention was necessary:
- Resolution (was the incident resolved spontaneously, or after discontinuing treatment):
- Date of Resolution:

The Principal Investigator and/or Investigators will review all adverse event reports to determine if specific reports need to be made to the IRB and FDA. The Principal Investigator and/or Investigators will sign and date the adverse event report when it is reviewed. For this protocol, only directly related SAEs/UPIRTSOs will be reported to the IRB.

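### The adverse event definition and two of its rules turn on a link to Nucala, conflict with other sections, and leave recording of unrelated events unclear

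*Combined protocol and SAP*

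**What the plan says.** Section 9.1 defines an adverse event as "An untoward or undesirable experience associated with the use of Nucala in a research subject". Serious events are a subset of adverse events and non-serious events are the remainder, so both carry this definition with them. New physical findings at the end of the study are recorded if they meet it.

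Two paragraphs of 9.1 then state a relatedness condition outright:
- Laboratory values: "Any clinical laboratory abnormality that can reasonably be related to the administration of Nucala should be documented as an adverse event".
- Hospital and surgical events: "Hospitalization, prolonged hospitalization, or surgery is to be reported as an adverse event if it can reasonably be related to use of Nucala".

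Section 9.2 sets the recording rule: "All adverse events occurring during the study period will be recorded". It adds nothing about recording irrespective of cause.

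Elsewhere the protocol treats relatedness as something other than part of the definition:
- Section 5.4.1, reasons for withdrawal: "Adverse Event: Patient experienced a related or unrelated event that would interfere with the study objectives/evaluation".
- Section 9.1, preexisting conditions: "A preexisting condition will be recorded as an adverse event if the frequency, intensity, or the character of the condition worsens", with no reference to Nucala.
- Section 9.2 follows each event until, among other end points, treatment or participation is found not to be the likely cause. It also sets a separate condition, a link that is at least possible, for immediate reporting of serious events.
- Section 9.3.1 lists among the CRF items for each event: "Relationship of the adverse event to the research".

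**The concern.** A safety table normally counts every untoward event and then shows which were thought related. If relatedness decides whether an event is an adverse event at all, that judgement is made before the data exist, one patient at a time. A pattern across patients, which is often what reveals a link, can then be lost before anyone can look for it.

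The design gives little means of correcting this. The study is open-label with a single arm (3.1), so there is no comparator. It has no primary safety endpoint (4.4) and no interim analysis (8.2). Medical monitoring under 9.6 reviews the number and type of serious adverse events, and so depends on what was classed as an adverse event in the first place. Under 5.4 withdrawn subjects are not followed, so a missed event may not be recoverable from them.

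**Working it through.** No arithmetic applies: the plan states no adverse event rate, and the point does not depend on sample size, power or alpha. The check is to read the provisions against each other.

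**Step 1. Does 9.2 settle the matter?** Its rule covers all adverse events, but that is the term defined in 9.1. If the definition excludes an event, 9.2 does not bring it back. So 9.2 cannot by itself show that unrelated events are captured.

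**Step 2. Is the definition causal?** A link with use of the drug can be read two ways.
- *Temporal:* the event happened while the subject was on the drug. Unrelated events are then included.
- *Causal:* the event is attributed to the drug. Unrelated events are then excluded.

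The definition does not say which is meant, and no text adds that an event counts whether or not it is considered related.

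**Step 3. Which reading do the other provisions support?**

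| Provision | Relatedness required to be an adverse event? |
|---|---|
| 9.1, laboratory abnormalities | Yes, stated |
| 9.1, hospitalization and surgery | Yes, stated |
| 9.1, worsened preexisting condition | No |
| 5.4.1, withdrawal for adverse event | No, unrelated events named |
| 9.2, follow-up until treatment is judged not the likely cause | No, an adverse event may prove non-causal |
| 9.2, separate relatedness condition for immediate serious event reporting | No, otherwise largely redundant |
| 9.3.1, relationship as a CRF item | No, otherwise largely redundant |

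The two groups cannot both follow from one definition.

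**Step 4. What survives under each reading?**
- *Causal:* events judged unrelated fall outside 9.1, against 5.4.1, 9.2 and 9.3.1.
- *Temporal:* most events are captured, but the laboratory and hospitalization/surgery paragraphs keep their own condition. A hospitalization judged unrelated is then not one that "is to be reported as an adverse event if it can reasonably be related to use of Nucala".

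Under both readings, 9.1 does not require a laboratory abnormality, hospitalization or operation judged unrelated to be treated as an adverse event. Under the causal reading the gap is wider. Two coordinators following the text in good faith could therefore record different data.

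**The case against.** The best case for the plan is that its working provisions already treat relatedness as an attribute of an event. An item for relationship, follow-up that may end in a finding of no causal role, and a withdrawal reason that names unrelated events make sense only if unrelated events are adverse events. The definition can be read as temporal. The two conditional paragraphs say when an event must be documented or reported, and do not forbid recording others. Hospitalization also stands in the list of serious events without its own relatedness test. In addition, 9.1 provides non-directed questioning at follow-up visits, 9.5 allows stopping on worsening linked in time to dosing, and 4.4 commits to Good Clinical Practice in tracking events.

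Much of this stands, and it rules out a stronger reading. A reader might infer that events thought unrelated can never be adverse events in this trial. The documents do not support that, because the provisions just listed say or imply otherwise. A reader might also infer that 9.1 gives the investigator the decision on association. It does not say who decides; 9.3 has the sponsor-investigator evaluate events, but only once they have been identified.

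What does not stand is the claim that these provisions cure the problem. They contradict the two conditional paragraphs without overriding them. The list of serious events is a list of adverse events, so an event must first qualify as one. Questioning and monitoring elicit and review events; they do not define which ones are entered.

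**Conclusion.** The point holds as an inconsistency with a practical consequence. Capture of events judged unrelated is ambiguous in general. For laboratory abnormalities, hospitalization and surgery, 9.1 does not require it.

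The direction of any bias is downward in the safety counts. Its size cannot be calculated: the documents give neither an expected event rate nor the share of events likely to be judged unrelated. A reader might take a given share of unrelated events as the same share of affected patients lost from the count. That does not follow, since a patient with several events stays in the count if any one of them is recorded. A reader might also suppose that a listed risk such as herpes zoster would be readily dismissed. The text does not support this: 1.6 names it as a risk and has subjects monitored for it.

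The conclusion assumes only that staff apply 9.1 as written. If the site in practice records everything, no data are lost, but the protocol does not secure that. The primary UAS7 analysis is unaffected. The change should be made because it is cheap and an unrecorded event cannot be re-assessed later.

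**What to change.** - In 9.1, define an adverse event as any untoward occurrence in a subject from the first dose to the last scheduled visit, whether or not considered related to Nucala. The first dose is at week 0, where the schedule table starts adverse event screening; add that item to the week 0 visit list in 7.2, which omits it.
- Remove the relatedness condition from the hospitalization and surgery paragraph.
- In the laboratory paragraph, replace it with new or worsened and clinically significant. Simply deleting the condition would make every out-of-range value an adverse event. The screening blood work in 7.1 supplies the comparison for week 10.
- Keep relationship as the existing CRF item in 9.3.1.
- State in 8.2 that all events and related events will be tabulated separately.

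The rules on what goes to the IRB can stay as they are, since they concern reporting and not recording. The cost is a wording change and a few more CRF entries in 20 patients. A single start at first dose leaves out events between screening and week 0, including any from the screening biopsy; the sponsor should accept that knowingly.

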9.2 Recording of Adverse Events

At each contact with the subject, the study team will seek information on adverse events by specific questioning and, as appropriate, by examination. Information on all adverse events should be

recorded immediately in the source document, and also in the appropriate adverse event section of the case report form (CRF). All clearly related signs, symptoms, and abnormal diagnostic, laboratory or procedure results will be recorded in the source document.

All adverse events occurring during the study period will be recorded. The clinical course of each event should be followed until resolution, stabilization, or until it has been ultimately determined that the study treatment or participation is not the probable cause. Serious adverse events that are still ongoing at the end of the study period must be followed up, to determine the final outcome. Any serious adverse event that occurs during the Adverse Event Reporting Period and is considered to be at least possibly related to the study treatment or study participation should be recorded and reported immediately.

9.3 Reporting of Serious Adverse Events and Unanticipated Problems

When an adverse event has been identified, the study team will take appropriated action necessary to protect the study participant and then complete the Study Adverse Event Worksheet and log. The sponsor-investigator will evaluate the event and determine the necessary follow-up and reporting required.

9.3.1 Sponsor-Investigator reporting: notifying the Mayo IRB

The Principal Investigator and/or Investigators will report, as soon as possible, but no later than 5 working days after first learning of the problem/event, to the Mayo Clinic IRB any UPIRTSOs and Non-UPIRTSOs according to the Mayo Clinic IRB Policy and Procedures.

Documentation of adverse events will include the following information collected in the adverse event section of the case report form (and entered into the research database):

- Subject's name:
- Medical record number:
- Disease:
- The date the adverse event occurred:
- Description of the adverse event:
- Relationship of the adverse event to the research:
- If the adverse event was expected:
- The severity of the adverse event (defined by a severity scale):
- If any intervention was necessary:
- Resolution (was the incident resolved spontaneously, or after discontinuing treatment):
- Date of Resolution:

The Principal Investigator and/or Investigators will review all adverse event reports to determine if specific reports need to be made to the IRB and FDA. The Principal Investigator and/or Investigators will sign and date the adverse event report when it is reviewed. For this protocol, only directly related SAEs/UPIRTSOs will be reported to the IRB.

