9.3.2 Sponsor-Investigator reporting: Notifying the FDA

This protocol is not being conducted under an FDA investigational new drug application.

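### Section 9.3.1 gives two incompatible rules for what goes to the IRB, and its undefined limit to directly related events is, on its natural reading, narrower than the possibly-related standard in 9.1 and 9.2

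*Combined protocol and SAP*

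**What the plan says.** Four sections of the combined protocol and SAP bear on this point.

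- **9.3.1, opening sentence.** The investigators are to report "to the Mayo Clinic IRB any UPIRTSOs and Non-UPIRTSOs according to the Mayo Clinic IRB Policy and Procedures", within 5 working days of learning of the event.
- **9.3.1, closing sentence.** For this protocol, "only directly related SAEs/UPIRTSOs will be reported to the IRB".
- **9.1, Definitions.** A UPIRTSO must be serious, unanticipated and related. The third criterion is met "if it is possibly related to the research procedures".
- **9.2, Recording of Adverse Events.** A serious adverse event in the reporting period that is "considered to be at least possibly related to the study treatment or study participation should be recorded and reported immediately". No recipient is named. The same section states: "All adverse events occurring during the study period will be recorded".
- **9.3, lead paragraph.** On who decides: "The sponsor-investigator will evaluate the event and determine the necessary follow-up and reporting required".

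Section 9.3.2 adds: "This protocol is not being conducted under an FDA investigational new drug application". The protocol does not define *directly related* or *Non-UPIRTSO*, and the IRB policy cited in 9.3.1 is not part of the documents.

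**The concern.** The opening and closing sentences of 9.3.1 answer the same question, what is sent to the IRB, and answer it differently. The closing sentence is the one tied to this protocol, it comes last and it says *only*. Study staff could reasonably take it as the working rule. If they do, relatedness is filtered twice: once at the level of possible, when 9.1 decides whether an event is a UPIRTSO, and again at the level of direct, when 9.3.1 decides whether it is sent.

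The wording matters more here than it might elsewhere. The study is single-arm and open-label, so there is no comparator against which to judge whether one event was caused by the drug, and attribution will often be uncertain. Section 9.5 has no numerical stopping limit and turns on worsening with an apparent temporal link to dosing, which is closer to possible than to direct attribution. Section 8.2 plans no interim analysis, 9.6 places safety oversight with the Principal Investigator, and there is no IND reporting route. Prompt notification of the IRB is therefore a safeguard whose scope should be clear.

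**Working it through.** No figure in the plan depends on this point and no arithmetic applies. The check is to run typical events through each rule. I assume that a Non-UPIRTSO is any event failing at least one of the three criteria in 9.1. In the closing-sentence column, *directly related* is first taken to qualify both SAEs and UPIRTSOs.

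| Event | UPIRTSO under 9.1? | 9.3.1 opening (subject to IRB policy) | 9.3.1 closing | 9.2 |
|---|---|---|---|---|
| A. Serious, unanticipated, directly related | Yes | Report | Report | Report immediately |
| B. Serious, unanticipated, possibly but not directly related | Yes | Report | Do not report | Report immediately |
| C. Serious, anticipated, possibly but not directly related | No | Report | Do not report | Report immediately |
| D. Non-serious | No | Report | Do not report | Record |

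For A to C the 9.2 column assumes that the event is a serious adverse event within the reporting period. Because 9.2 names no recipient, that column shows a relatedness threshold and not an IRB rule.

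**Scope.** Rows B, C and D are included by the opening sentence and excluded by the closing one. Only row A gets the same answer from both.

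**Relatedness.** Row B is the important one. The event satisfies all three criteria in 9.1, so the protocol itself calls it a UPIRTSO, yet the closing sentence drops it.

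**Do other readings of the closing sentence remove the conflict?**

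1. *Directly related* qualifies SAEs alone. Row B is then reported as a UPIRTSO. Rows C and D still differ between the two sentences, so the conflict in scope remains.
2. *Directly* means no more than possibly. The word then adds nothing for UPIRTSOs, which are already possibly related by definition. Rows B and C are reported, but row D still differs.
3. *Directly* means direct as opposed to indirect, and not a higher degree of certainty. Section 9.1 makes no such distinction, so indirectly related events would still be UPIRTSOs that the closing sentence excludes.

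No reading of the closing sentence alone makes the two sentences of 9.3.1 agree.

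**The case against.** The strongest reply has four parts.

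*The opening sentence is not a rule to report everything.* It is bounded by the IRB's own policy, which may narrow what must be sent, particularly among Non-UPIRTSOs. This stands, and it means that rows C and D may conflict less in practice than the table shows. It does not remove the closing sentence, which adds its own limit for this protocol.

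*The qualifier may attach to SAEs alone.* A second relatedness test on events already defined as related would be odd, so perhaps every UPIRTSO is still reported. This reading is possible and would rescue row B. It has to be supplied by the reader, however, and it leaves the difference in scope.

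*Section 9.2 is not shown to be an IRB rule.* This is correct. Its value here is as evidence that the protocol elsewhere sets the bar for reporting serious events at possible.

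*Detection and care are unaffected.* All events are recorded and followed, 9.3 has the team act to protect the participant, and investigators review and sign adverse event reports. This also stands: the gap is in notification of the IRB.

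A reader might go further and infer that IRB reporting is the only independent check on safety. The documents do not support that: 11.1 provides for a monitor or quality assurance reviewer with access to study documents, and 11.2 for audits and inspections by the IRB, the sponsor and government agencies. Neither section sets a schedule or an event that triggers review, so they are no substitute for prompt notification, but they exist.

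**Conclusion.** The point holds as an inconsistency in the reporting rule. Section 9.3.1 contradicts itself on scope. On its natural reading the closing sentence also sets a stricter relatedness bar than the definition in 9.1 and the threshold in 9.2. A serious, unanticipated, possibly related event could therefore go unreported to the IRB while being recorded and followed.

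The conflict in scope rests on the text alone, subject to whatever limits the IRB policy sets. The loss of row B further assumes that *directly related* qualifies UPIRTSOs as well as SAEs and means something narrower than *possibly related*.

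The size cannot be estimated. It is tempting to say that every serious event graded possible or probable would be lost, but 9.3.1 asks only for the relationship to the research and provides no grades. It is equally tempting to express one event as a share of the 20 patients, but that describes the sample size and says nothing about how many reports would be missed. Nor do the documents show that any event was in fact kept from the IRB. The matter should be corrected because it is safety-relevant and cheap to put right; it does not affect the efficacy analysis.

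**What to change.** Delete the closing sentence of 9.3.1. The opening sentence then governs, with its 5-working-day limit, the IRB policy it cites and the possibly-related criterion from 9.1.

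If a limit specific to this protocol is wanted, reword the closing sentence so that it covers all UPIRTSOs and all serious adverse events at least possibly related to treatment or participation. Then bring the reference to Non-UPIRTSOs in the opening sentence into line with it. Replacing only the word *directly* would not be enough: a rule limited to SAEs and UPIRTSOs would still stand against one that also names Non-UPIRTSOs.

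The change is one sentence, or two if a limit is kept. It may produce some additional IRB reports in a 20-patient study. How many depends on the IRB policy and on the events that occur, neither of which can be seen from the documents.
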